### **Patient Reported Outcomes (PRO)**

Health-related quality of life and symptom assessments will be performed per [Appendix C](#) and [Appendix D](#), Study Assessments using the EORTC QLQ-C15-PAL, the EORTC QLQ-LC13, and the European Quality of Life-5 Dimensions (EQ-5D-5L).

The European Organization for Research and Treatment of Cancer Quality of Life Questionnaire (EORTC QLQ-C15-PAL) is a shortened version of the EORTC QLQ-C30, a widely used instrument for measuring QOL in cancer research. It was developed to ease the difficulty of completing long surveys in subjects who may have a high

symptom burden and short life expectancy. The QLQ-C15-PAL questionnaire contains four multi-item scales (physical & emotional functioning, fatigue and pain) along with six individual items (nausea & vomiting, dyspnea, insomnia, appetite loss, constipation, and global quality of life).

The EORTC QLQ-LC13 is a lung cancer specific module which will supplement the EORTC QLQ-C15-PAL, resulting in a 28-item disease and cancer site-specific quality of life and symptom questionnaire. The QLQ-LC13 module items evaluate symptoms such as cough, haemoptysis, shortness of breath, sore mouth or tongue, dysphagia, tingling hands or feet, hair loss, and pain.

The EuroQol 5 Dimensions 5 Level (EQ-5D-5L) is a generic preference instrument that has been validated in numerous populations. The EQ-5D-5L is composed of 5 questions and a visual analog scale (VAS) assessing overall health that can be converted into a single health status or "utility" score for use in an economic evaluation to adjust life-years gained by the subject's health-related quality of life.

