#### **8.1.6 Patient Reported Outcomes (PROs)**

The EORTC QLQ-C15-PAL/LC13 scoring manual will be used to transform the raw scores into the domain scores (global health, functional scales, symptom scales/items). Physical functioning domain of the QLQ-C15-PAL PRO questionnaire is a secondary endpoint in the hypothesis testing hierarchy (see Section 8.3). The other scales will be analyzed on an exploratory basis. Change from baseline of the items and domains of the QLQ-C15-PAL/LC13 will be summarized by treatment arm. The EQ-5D-5L manual and the published weights will be used to convert the individual items to the utility scores. Change from baseline of the EQ-5D-5L utility score and VAS will be summarized by treatment arm.

Treatment group differences will be evaluated by analyzing the change from baseline using a one-way analysis of variance (ANOVA) model. Proportion of subjects with clinically meaningful worsening in physical functioning will be compared between the treatment arms.

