Distribution of the duration of response will be estimated for each treatment arm using Kaplan-Meier methodology. Median duration of overall response with corresponding 95% CI for each treatment arm will be provided. Due to the non-randomization nature of the analysis set for DOR, the analysis of DOR will be considered descriptive and will not be compared between treatment arms.

Patients Reported Outcomes (PRO)

The endpoints based on subject self-reported health related quality of life (QoL) and symptom assessments will be analyzed for post-treatment Week 3, Week 7 and subsequently with the increment of 6 weeks (i.e., Week 13, Week 19, and Week 24). The EORTC QLQ-C15-PAL/LC13 and the European Quality of Life-5 Dimensions (EQ-5D-5L) are used to measure the QoL and symptom assessments.

QLQ-C15-PAL & QLQ-LC13

The QLQ-C15-PAL is an abbreviated 15-item version of the EORTC QLQ-C30 for palliative care. The QLQ-C15-PAL questionnaire has four abbreviated scales measuring physical functioning, emotional functioning, nausea and vomiting, and fatigue. These

scales are estimated using the algorithm specified in *Addendum to the EORTC QLQ-C30 Scoring Manual: Scoring of the EORTC QLQ-C15-PAL* (July, 2006).

For each scale in QLQ-C15-PAL questionnaire, the raw score (RS) is computed as the mean of component items over the number of items answered for that scale if at least 50% of the items are answered, and set as missing otherwise. Then the scale score (SS) will be computed as:

$$SS = \{(RS - 1)/range\} \cdot 100.$$

The lung cancer module (QLQ-LC13) is composed of one multi-item scale to assess dyspnea, and a series of single items assessing coughing, sore mouth, dysphagia, peripheral neuropathy, alopecia, hemoptysis, and pain.

All scales and single items are reported on categorical responses, and will be linearly converted to 0 through 100 numeric values. Given a scale, the raw score (RS) is computed as the mean of component items over the number of items answered for that scale if at least 50% of the items are answered. It will be set as missing otherwise. Then the scale score, $SS = \{(RS - 1)/range\} \cdot 100$, will be computed.

For single-item measures (dyspnea, insomnia, appetite loss, constipation, diarrhea, and financial difficulties), none of the single-item measures can be computed if not answered. If a scale score cannot be computed, the outcome for that score is left blank.

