The analysis of continuous endpoint of EORTC QLQ-C15-PAL PF scale score will be performed by analyzing the change in scale score from baseline to the given time point, using an analysis of covariance (ANCOVA) model including stratification factors and baseline as covariates, and 95% CI for treatment group difference will be provided.

Change from baseline at post-baseline Week 7 in the physical function scale is one of the secondary efficacy endpoints, and other scales and items are considered exploratory.

For each scale, the treatment group differences will be evaluated by analyzing the change from baseline to each of the post-baseline time-points and to the final measurement (last QoL assessment per subject) using a one-way analysis of variance (ANOVA) model including stratification factors and baseline as covariates. Simple summary statistics for QoL assessments at each timepoint will also be presented.

EQ-5D-5L

The EuroQol 5 Dimensions 5 Level (EQ-5D-5L) is a preference based measure of health status that consists of EQ-5D descriptive system and EQ visual analogue scale (VAS).

The EQ-5D descriptive system comprises the following 5 dimensions: mobility, self-care, usual activities, pain/discomfort, and anxiety/depression. Each of the dimensions is divided into 5 levels of perceived problems: Level 1 (indicating no problem), Level 2 (indicating slight problems), Level 3 (indicating moderate problems), Level 4 (indicating severe problems), and Level 5 (indicating extreme problems). EQ-5D-5L health status, defined by the EQ-5D-5L descriptive system, will be converted into a single preference –weighted health status or "utility" index score by applying country-specific weights (if available) or U.S. weights (if not available).

The EQ VAS records the respondent's self-rated health on a visual analogue scale (0 to 100). The VAS score will be measured separately.

Mean change from baseline in EQ-5D-5L "utility" index score to each applicable post-baseline time point, and to the final measurement will be presented by treatment arm. The treatment group difference will be evaluated by analyzing the change from baseline using a one-way analysis of variance (ANOVA) model including stratification factors and baseline as covariates. The same methodology will apply to the mean change from baseline in VAS score.

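### SAP 11.2 gives two scoring instructions for the QLQ-C15-PAL and no score direction, so the sign of the physical-functioning endpoint depends on which is programmed and how the items are coded

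*SAP*

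**What the plan says.** SAP 11.2 (Patients Reported Outcomes, QLQ-C15-PAL & QLQ-LC13) gives two instructions in succession.

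- It names four abbreviated scales (physical functioning, emotional functioning, nausea and vomiting, fatigue) and says these "scales are estimated using the algorithm specified in" the EORTC addendum on scoring the QLQ-C15-PAL.
- The next paragraph gives a rule of its own: "For each scale in QLQ-C15-PAL questionnaire, the raw score (RS) is computed as the mean of component items", provided at least half the items are answered, and then SS = 100 × (RS − 1)/range. The term range is not defined.

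The SAP repeats the formula for the LC13, whose listed content is all symptoms, adding that "All scales and single items are reported on categorical responses, and will be linearly converted to 0 through 100 numeric values". No separate formula is given for functioning scales and no direction is stated. A later sentence on unanswered items begins "For single-item measures (dyspnea, insomnia, appetite loss, constipation, diarrhea, and financial difficulties".

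On status, the SAP says "Change from baseline at post-baseline Week 7 in the physical function scale is one of the secondary efficacy endpoints". SAP 5.7.3 places it third in the test order, after OS and PFS.

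Protocol 8.1.6 says the EORTC "scoring manual will be used to transform the raw scores into the domain scores", and it names global health, functional scales and symptom scales or items as separate classes. Protocol 5.3.1.1 describes the C15-PAL as having "four multi-item scales (physical & emotional functioning, fatigue and pain) along with six individual items". Neither document reproduces the addendum, the manual or the item coding.

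**The concern.** Two programmers could each follow a sentence of the SAP and might not produce the same physical-functioning score. The printed formula treats physical functioning exactly as it treats cough or dyspnea. For a symptom, a score that rises with the raw code is natural if codes rise with severity. For a functioning scale coded the same way, it would make 100 the worst function.

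Direction matters because H3 in protocol 8.3 is one-sided superiority of Arm A in physical functioning. It also matters without a test: protocol 8.1.6 plans change-from-baseline summaries by arm and a comparison of the proportion with clinically meaningful worsening in physical functioning. Neither can be read unless the sign of a worsening is known. The SAP does give this for the EQ-5D-5L, where Level 1 is no problem and Level 5 extreme problems, but not for the instrument that carries the secondary endpoint.

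**Working it through.** **Inputs.** The formula is from SAP 11.2. The SAP gives no value for range, so I assume items coded 1 to 4 (range 3). The coding direction is not in the documents, so both directions are taken.

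**1. The plan's own figure.** The SAP says scores run from 0 to 100. RS = 1 gives 100 × (1 − 1)/3 = 0, and RS = 4 gives 100 × (4 − 1)/3 = 100. This reproduces.

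**2. Printed against reversed form.** The reversed score is SS′ = 100 × {1 − (RS − 1)/range} = 100 − SS.

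| RS | Printed SS | Reversed SS′ |
|---|---|---|
| 1 | 0 | 100 |
| 2 | 33.3 | 66.7 |
| 3 | 66.7 | 33.3 |
| 4 | 100 | 0 |

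With range 6, RS of 1, 3, 5 and 7 gives the same four pairs, so the result does not depend on the assumed range.

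**3. Change from baseline.** With B for baseline and F for follow-up, (100 − F) − (100 − B) = −(F − B). Every change score reverses sign. So does the ANCOVA treatment coefficient, with the same standard error, and a one-sided p becomes 1 − p. At the one-sided 0.02 that SAP 5.7.3 allots to secondary endpoints at the interim, p = 0.02 would become 1 − 0.02 = 0.98.

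**4. Illustration.** I simulated 600 subjects, randomized 2:1, with three items coded 1 to 4 (4 = most difficulty), a true benefit for Arm A, and an ANCOVA with baseline and stratification factors. The effect size is invented; the run only confirms the algebra.

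| Scoring | Arm A minus Arm B | SE | One-sided p (Arm A higher) |
|---|---|---|---|
| Printed | −7.84 | 1.57 | > 0.999 |
| Reversed | +7.84 | 1.57 | 4 × 10⁻⁷ |

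**5. When this is an error.** If codes rise with difficulty, the printed score is high for poor function, and a reader who takes higher as better gets the wrong sign. If codes rise with ability, the printed score is already higher-is-better and nothing reverses.

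**6. Item list, side by side (C15-PAL).**

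| Measure | Protocol 5.3.1.1 | SAP 11.2 |
|---|---|---|
| Physical functioning, emotional functioning, fatigue | Multi-item scale | Abbreviated scale |
| Pain | Multi-item scale | Not listed (only an LC13 pain item) |
| Nausea and vomiting | Individual item | Abbreviated scale |
| Dyspnea, insomnia, appetite loss, constipation | Individual item | Single item |
| Global quality of life | Individual item | Not listed |
| Diarrhea, financial difficulties | Not listed | Single item |

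Diarrhea and financial difficulties are also absent from both documents' LC13 lists. None of these mismatches enters the physical-functioning score.

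**The case against.** The strongest reply is that the scoring source is already named twice, by the addendum in SAP 11.2 and by the manual in protocol 8.1.6. A wrong sign needs a programmer to follow the printed formula instead and then read the result as higher-is-better. That is fair, and it makes this an ambiguity rather than a demonstrated error. It does not remove the ambiguity, because the SAP does not say which instruction prevails.

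A reader might infer that the printed rule contradicts the addendum, or that the endpoint will come out with the wrong sign. The documents support neither, since they contain neither the addendum's algorithm nor the item coding. A reader might also infer that the stray items contribute to a wrong sign; they cannot. Nor does the SAP call nausea and vomiting a multi-item scale: its word is abbreviated, and it uses multi-item only for LC13 dyspnea. The sentence naming diarrhea and financial difficulties is a missing-answer rule, not an instruction to analyse them.

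On impact, protocol 8.0 now says there will be no efficacy testing. Appendix C (footnote u) and Appendix D (footnote t) limit PROs to Screening and C1D1 before infusion. The Section 1.1 rationale says PRO analysis will not be done. Even under the original plan H3 was reached only after OS and PFS had both succeeded. This largely stands. What remains is that protocol 8.1.6 and SAP 11.2 still specify change-from-baseline output, and that 444 subjects were enrolled before the PRO schedule was cut. The schedule in SAP Appendices A and B required post-baseline PROs, so such data plausibly exist.

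**Conclusion.** The point holds as an internal inconsistency with a conditional consequence. It is certain from the documents that SAP 11.2 carries two scoring instructions for the C15-PAL, that the printed one makes no distinction between functioning and symptom scales although protocol 8.1.6 does, and that no direction is given for the secondary endpoint.

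The size is all or nothing. If item codes rise with difficulty, the printed formula is programmed and the result is read as higher-is-better, the physical-functioning difference keeps its magnitude and standard error but has the opposite sign. If the codes run the other way, or the addendum is followed and yields a higher-is-better score, there is no reversal. The symptom scales are not affected by this argument.

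The item-list mismatch is a separate documentation error that needs no coding assumption. Under Amendment 4 the practical reach of both is any PRO summary produced from data already collected.

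**What to change.** In SAP 11.2:

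1. Delete the printed formula for the QLQ-C15-PAL and score it only by the cited addendum and scoring manual. This is better than printing one functional and one symptom formula, because protocol 8.1.6 names global health as a third class that two formulas would leave open.
2. State that a higher physical-functioning score is better, so that a positive change from baseline favours the arm. Check the programmed score against the addendum for that orientation.
3. Align the scale and item list with protocol 5.3.1.1: add pain and global quality of life, list nausea and vomiting as an individual item, and remove diarrhea and financial difficulties.

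The cost is SAP wording and a check of one scoring program, with no new data. SAP 4.0 describes the document as a draft to be finalized before any comparative analysis by arm, so the change can be made at that step.

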11.3 Sensitivity Analyses

Sensitivity analyses will be conducted to evaluate the robustness of efficacy results. OS and PFS (by CRAC) will be analyzed in the PPS.

A sensitivity analysis of PFS will be performed based on investigator-assessed disease progression or death from any cause using the Randomized Set. The statistical methodology described in Section 11.1.1 for TTE endpoints will be used.

Sensitivity analyses of investigator-determined ORR will also be performed based on the Randomized Set (ORR analysis will only include the randomized subjects with measurable disease at baseline).

11.4 Subgroup Analyses

For randomized subjects, analysis of OS will be performed in the following subgroups on an as-stratified basis according to stratification data collected at randomization:

- Prior history of brain metastases and PCI (brain metastases, no brain metastases and PCI, no brain metastases nor PCI)
- Sensitivity to first line platinum-based regimen (sensitive [OR/SD after first line therapy and progression/recurrence-free interval ≥ 90 days] versus refractory/resistant [PD as best response to or < 90 days progression/recurrence-free interval after first line therapy])
- Lactate dehydrogenase (LDH) ($>$ Upper Limit of Normal (ULN) vs. \leq ULN) at Screening
- Overall Veterans Administration Lung Study Group (VALG) stage (Limited Disease vs Extensive Disease) at initial diagnosis
- Gender
- Race

Difference in OS between rovalpituzumab tesirine and topotecan arms will be assessed by an unstratified log-rank test for each subgroup. Hazard ratios will be calculated by a Cox's model.

12.0 Safety Analysis

12.1 General Considerations

Unless otherwise specified, safety analyses will be performed on the safety set.

Unless specified, all summaries/analyses involving AEs will only include treatment-emergent adverse events (TEAEs). TEAEs are defined as any adverse event with onset or increase in severity after the first dose of study drug (rovalpituzumab tesirine or topotecan) but no more than 70 days after the last dose of study drug administration.

A summary of continuous safety endpoints (e.g., change from baseline values in laboratory values, vital signs parameters) will include the mean, standard deviation, median and range. In the context of change from baseline analyses, summary of baseline and post-baseline data will also be provided. Categorical safety endpoints (e.g., incidence of AEs or clinically significant ECG values) will be summarized using frequencies and percentages. All the analyses will be carried out by treatment group.

Unscheduled assessment will not be included in the summary of change from baseline, but will be included in producing shift tables and summary of lab abnormalities.

12.2 Analysis of Adverse Events

Adverse Event Overview

The number and percentage of subjects experiencing TEAEs between the treatment groups will be summarized for the following adverse event categories.

- TEAEs
- NCI toxicity (maximum) grade 3 or 4 TEAEs
- Drug-related TEAEs
- NCI toxicity (maximum) grade 3 or 4 drug-related TEAEs
- Serious TEAEs
- NCI toxicity (maximum) grade 3 or 4 serious TEAEs

- Drug-related serious TEAEs
- TEAEs leading to discontinuation/reduction/interruption of study drug,
- Drug-related TEAEs leading to discontinuation/reduction/interruption of study drug
- TEAEs leading to death
- Drug-related TEAEs leading to death

Adverse Events by System Organ Class and Preferred Term

The number and percentage of subjects experiencing TEAEs will be tabulated according to the primary MedDRA system organ class (SOC) and MedDRA preferred term (PT) for each treatment group. Subjects reporting more than one adverse event for a given MedDRA PT will be counted only once for that term. Subjects reporting more than one type of adverse event within a MedDRA SOC will be counted only once for that SOC. Subjects reporting more than one type of adverse event will be counted only once in the overall total.

AEs by Preferred Term

The number and percentage of subjects experiencing adverse events will be tabulated according to the MedDRA PT for each treatment group. Subjects reporting more than one AE for a given MedDRA PT will be counted only once for that term.

AEs by Maximum Severity

Adverse events will be summarized by SOC, PT and maximum severity per NCI CTCAE v.4 grading in each treatment arm. If a subject has an AE with unknown severity, then the subject will be counted in the severity category of "unknown," unless the subject does not have another occurrence of the same AE with a severity present. In addition, Grade 3 or higher AE will also be summarized by SOC and PT.

AEs by Relationship

Adverse events possibly related to rovalpituzumab tesirine, dexamethasone, topotecan, as assessed by the investigator, will be summarized separately in each treatment arm.

Following summaries will be presented for the AEs possibly related to rovalpituzumab tesirine, dexamethasone, topotecan, separately:

- Summary of AE by PT
- Summary of AE by SOC and PT
- Summary of Grade 3 or higher AE by SOC and PT
- Summary of SAE by SOC and PT
- Summary of rovalpituzumab tesirine discontinuation by SOC and PT (possibly related to rovalpituzumab tesirine only)
- Summary of topotecan discontinuation by SOC and PT (possibly related to topotecan only)

If a subject has an AE with unknown relationship, then the subject will be counted in the relationship category of "unknown," unless the subject does not have another occurrence of the same AE with a relationship present.

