### **6.1.2 Adverse Event Severity**

The investigator will rate the severity of each adverse event according to the National Cancer Institute Common Terminology Criteria for Adverse Events (NCI CTCAE Version 4.0). If a reported adverse event increases in severity, the initial adverse event should be given an outcome date and a new adverse event reported on a different date from the end date of the previous adverse event to reflect the change in severity. For all reported serious adverse events that increase in severity, the supplemental eCRFs also need to be updated to reflect the change in severity.

When CTCAE criteria cannot be used, the event should be graded as defined below:

- |                  |  |
|------------------|--|
| Grade 1   | The adverse event is transient and easily tolerated by the subject (mild).   |
| Grade 2   | The adverse event causes the subject discomfort and interrupts the subject's usual activities (moderate).                                      |
| Grade 3/4 | The adverse event causes considerable interference with the subject's usual activities and may be incapacitating or life-threatening (severe). |
| Grade 5   | The adverse event resulted in death of the subject (severe).   |

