### 6.1.4 Deaths

For SAEs with the outcome of death, the date and cause of death will be recorded on the appropriate case report form.

Deaths that occur during the protocol specified AE reporting period (Section 6.1.6) that are more likely related to disease progression will therefore be considered as an expected SAE and will not be subject to expedited reporting. These events should be recorded on the AE eCRF as described in Section 6.1.1.3. After the AE reporting period, deaths

attributed to progression of disease under study should be not be recorded on the AE eCRF.

Death should be considered an outcome and not a distinct event. The event or condition that caused or contributed to the fatal outcome should be recorded as the single medical concept on the AE eCRF. Generally, only one such event should be reported. The term "sudden death" should only be used for the occurrence of an abrupt and unexpected death due to presumed cardiac causes in a patient with or without pre-existing heart disease, within 1 hour of the onset of acute symptoms or, in the case of an unwitnessed death, within 24 hours after the patient was last seen alive and stable. If the cause of death is unknown and cannot be ascertained at the time of reporting, "unexplained death" should be recorded on the AE eCRF. If the cause of death later becomes available (e.g., after autopsy), "unexplained death" should be replaced by the established cause of death.

[figure not shown]

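### Three Adverse Event Overview rows stop at maximum Grade 4, so subjects whose worst event is fatal leave the severe-toxicity count and the rows disagree with the Grade 3 or higher tables in the same section (minor)

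*SAP*

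**What the plan says.** SAP 12.2, Adverse Event Overview, lists 11 categories to be summarised as numbers and percentages of subjects by arm. Three are limited by grade: "NCI toxicity (maximum) grade 3 or 4 TEAEs", "NCI toxicity (maximum) grade 3 or 4 drug-related TEAEs" and "NCI toxicity (maximum) grade 3 or 4 serious TEAEs". No overview row covers Grade 3 or higher. Two rows cover events leading to death, one for all treatment-emergent adverse events (TEAEs) and one being "Drug-related TEAEs leading to death".

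Elsewhere the same section uses a different limit. Under maximum severity it says "In addition, Grade 3 or higher AE will also be summarized by SOC and PT". Under relationship to each drug it lists "Summary of Grade 3 or higher AE by SOC and PT". SAP 12.3.2 adds a listing of Grade 3 or higher events and a listing of fatal ones. SAP 12.3.3 adds a summary of deaths by arm, split at 70 days after treatment.

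Protocol 6.1.2 places an event that results in death at Grade 5, in the scale for events that CTCAE criteria do not cover. Protocol 6.1.4 brings deaths more likely due to progression, if they fall in the reporting period, into the adverse event data: "These events should be recorded on the AE eCRF as described in Section 6.1.1.3". SAP 12.1 ends the treatment-emergent window 70 days after the last dose.

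**The concern.** A row built on the subject's maximum grade and capped at 4 gives an odd result when events are fatal. A subject with Grade 4 toxicity who then has a fatal TEAE moves from a maximum of 4 to a maximum of 5 and leaves the row. A subject whose only severe event was fatal never enters it. With everything else equal, an arm's severe-toxicity percentage then falls as its fatal events rise.

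This matters more than usual here. Fatal TEAEs need not be rare, because progression deaths in the window go on the adverse event form. Comparing safety between arms is a stated exploratory objective, and enrollment was stopped over survival concerns with the study drug. The overview is also the table most readers look at first, and section 12.2 does not explain why its limit differs from that of the detailed tables.

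**Working it through.** The plan states no figure that depends on these rows, so there is nothing to reproduce. The check is of the counting rule.

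**Step 1: the identity.** Within one category and arm, let G3 be the proportion of subjects with a maximum grade of 3 or higher, and G5 the proportion with a maximum of 5. On the literal reading:

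row = G3 − G5

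For fixed G3, each added point of G5 lowers the row by one point.

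**Step 2: the difference between arms.** Write D3 and D5 for the Arm A minus Arm B differences in G3 and G5. The difference shown in the row is D3 − D5. If D3 is positive, the order of the arms reverses only when D5 exceeds D3. If D5 is zero, the difference is not distorted.

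**Step 3: who leaves which row.** Protocol 6.1.1.2 makes a fatal event serious, so a fatal TEAE removes the subject from both the all-event and the serious rows. It removes the subject from the drug-related row only if the fatal event is itself judged drug-related. A subject with a Grade 3 or 4 drug-related event and an unrelated fatal event stays in that row. A fatal event with onset more than 70 days after the last dose is not treatment-emergent and removes nobody.

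**Step 4: illustration.** The documents give no Grade 3 or higher or Grade 5 rates by arm for this trial. All rates below are assumptions, in percent, Arm A / Arm B.

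| G3 | G5 | Row = G3 − G5 | D3 | Difference in row |
|---|---|---|---|---|
| 65 / 65 | 10 / 10 | 55 / 55 | 0 | 0 |
| 65 / 60 | 15 / 13 | 50 / 47 | +5 | +3 |
| 70 / 55 | 20 / 10 | 50 / 45 | +15 | +5 |
| 65 / 60 | 20 / 10 | 45 / 50 | +5 | −5 |
| 65 / 65 | 20 / 10 | 45 / 55 | 0 | −10 |
| 65 / 80 | 25 / 10 | 40 / 70 | −15 | −30 |

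The distortion can be absent, shrink a real difference, reverse it, create one or widen one. For scale, the 444 subjects enrolled (Protocol 8.4) split 2:1 give 296 and 148, if all were treated. In the fourth line the row would show 0.45 × 296 = 133 and 0.50 × 148 = 74 subjects.

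**Step 5: can the other rows repair it?** Row + G5 = G3, so adding the leading-to-death row recovers the Grade 3 or higher rate (45 + 20 = 65 and 50 + 10 = 60 in the fourth line). This holds if every TEAE leading to death is graded 5, which the SAP does not state.

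**The case against.** The strongest reply is that nothing is lost. On the literal reading, maximum Grade 3 or 4 and maximum Grade 5 are separate groups, and the second has its own rows in the same table. The detailed tables include Grade 5. If the Grade 3 or higher table carries an overall total, as the main table by system organ class and preferred term does, that total is the missing figure. Most of this stands, and it is why the point is minor. What remains is that the reader must do the addition and assume that every event leading to death is Grade 5. Serious events also have no Grade 3 or higher table, because the serious event summaries carry no grade limit.

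A second reply is that the maximum might be taken per preferred term, so that Grade 4 neutropenia would still count despite a separate fatal event. Protocol 8.2.1 and the maximum-severity table work that way. The overview counts subjects by category, however, and the SAP does not state a per-term rule for it. At the least, the row needs a definition.

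A reader might go further and infer that every subject with a fatal event drops out of all three rows. Step 3 shows that this fails for the drug-related row.

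A reader might also size the effect from the planning medians. With exponential survival over 112 days (second dose on day 43 plus about 70 days), 1 − 0.5^(112/(8.67 × 30.4375)) = 25% and 1 − 0.5^(112/(6.5 × 30.4375)) = 32% would die in the window. The documents do not support that use. The window assumes two Arm A doses, whereas topotecan runs in 21-day cycles until progression. Subjects given one dose have a shorter window: at 71 days the same formula gives 17% and 22%. Not every death will be recorded as a fatal TEAE. On those inputs Arm B would also lose more subjects than Arm A, so they do not show that the study drug would look safer.

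**Conclusion.** The point holds as a minor fault of definition and consistency. Three of 11 overview rows, read literally, leave out subjects whose maximum grade in the category is 5, while the tables in the same section use Grade 3 or higher. The rows therefore depend on fatal event rates, point for point.

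It would be tempting to conclude that the arm with more deaths will look less toxic. The documents do not support that as a general statement. A reversal needs a Grade 5 difference larger than the Grade 3 or higher difference, and no rates by arm are given. Nor is fatal toxicity concealed, since the rest of the safety package reports it. The size is unknown, and 45% versus 50% in place of 65% versus 60% is an illustration on assumed rates. The rows are descriptive, and no test, sample size or decision rule rests on them.

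**What to change.** In the SAP 12.2 overview, redefine the three rows as maximum Grade 3 or higher for all, drug-related and serious TEAEs. Keep the two leading-to-death rows. State that the maximum is taken per subject within each category and that Grade 5 is included. If the sponsor wants fatal and non-fatal severity kept apart, show maximum Grade 3, 4 and 5 as separate lines under each total.

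The cost is a row label and a programming filter. No new data are needed, and no other analysis changes.
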